7. SAMPLE SIZE AND STATISTICAL METHODS

7.1 Determination of Sample Size

As stated above, based on the results of our prospective observational study of blinded CGM placement at time of one-hour GCT of pregnant people ≤ 30 weeks

#UTHealth

IRB NUMBER: HSC-MS-22-0153 IRB APPROVAL DATE: 07/05/2023 gestation we would like to adjust the sample size for this trial. A CGM metric of time above range ≥ 10% was associated with higher rates of adverse neonatal outcomes of preterm birth, intravenous glucose therapy and longer hospitalization. The findings of this study serves as the basis of diagnosis of GDM through CGM for our trial. Based on the results of this prospective trial the estimated rate of the primary outcome was 40%. In this trial we would include a more diverse population with a lower rate of factors associated with GDM such as lower BMI, different race and ethnicity. Our assumption is that the rate of the primary outcome will be 25%.

Sample size calculations using a Bayesian analysis with different probability thresholds are presented in Table 4. In order to detect a 30% reduction in the rate of adverse neonatal outcome between the control and intervention with 90% power and a Bayesian posterior probability of 75% (of any reduction), 734 individuals (367 per group) will need to be diagnosed with GDM. With a 10% loss to follow up, 816 people in total will need to be enrolled. A total of 1020 individuals would need to be approached, to accommodate an expected enrollment rate of 80%.

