7.2 Statistical and analysis plan

An intention to treat analysis will be conducted. All outcomes will be analyzed using generalized linear models (GLMs) and will include stratifying variables of BMI and clinic site as covariates. Primary outcome and all other binary outcomes will be analyzed with a logistic model. Secondary outcomes will be analyzed using appropriate distributional assumptions, i.e. negative binomial for counts and normal for continuous outcomes. We will report relative risks or group mean differences and 95% confidence intervals (CIs). Differences in costs will be assessed using a generalized linear model (GLM) with log-

link and gamma distribution. We will also compute the incremental cost-effectiveness ratio (ICER) of the total health system costs (savings) per prevented mother-infant dyad from developing an adverse outcome using a joint GLM with log link for costs and probit for maternal or neonatal adverse outcomes. We will induce dependency between costs and the adverse outcomes through shared random effects in the joint model.

Planned Bayesian analysis:

We will also conduct a Bayesian analysis of the primary outcome and of costs and cost-effectiveness. Sample size calculations using a Bayesian analysis with different probability thresholds are presented in Table 4. The composite primary outcome will be evaluated with a Bayesian binomial model. Finally, we conservatively set a neutral prior probability centered at a relative risk (RR) of 1.0 (*i.e.*, a priori no effect on the outcome) and a 95% credible interval of 0.3-3.3 encompassing the largest likely effect size for major outcomes in randomized trials. This neutral prior will also be used to assess cost differences between the two treatment groups. Finally, we will report RR and 95% credible intervals and the probability of reduced adverse neonatal outcomes and costs, as well as the probability that the ICER will fall in the dominant quadrant of the cost-effectiveness plane (Figure 1).

Table 4: Bayesian power to declare efficacy depending on level of evidence (probability threshold)

Control Rate	Treatment Rate	# patients /group	Prob(RR<1) > specified threshold					
			70%	75%	80%	85%	90%	95%
0.4	0.24	60	0.92	0.89	0.85	0.79	0.71	

	0.75	0.82	0.85	0.89	0.93	120	0.28	0.4
	0.90	0.93	0.96	0.98	0.98	110	0.24	0.4
	0.90	0.94	0.96	0.97	0.98	210	0.28	0.4
0.80	0.89	0.93	0.95	0.97	0.98	236	0.245	0.35
0.80	0.89	0.93	0.95	0.97	0.98	294	0.21	0.30

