0.80	0.89	0.93	0.95	0.97	0.98	367	0.175	0.25
0.80	0.88	0.92	0.95	0.96	0.97	484	0.14	0.20

Interim analysis after 50% enrollment will be performed to assess the frequency of the primary and secondary outcomes. At that point, a decision will be made to see if there is a need to adjust the sample size.

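### Section 7.1 claims 90% power at a 75% posterior probability for 367 per group, but Table 4 gives 97% for that cell and section 7.2 sets no success threshold

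*Combined protocol and SAP*

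**What the plan says.** Section 7.1 assumes a 25% rate of the composite neonatal outcome. It sets the target as follows: "In order to detect a 30% reduction in the rate of adverse neonatal outcome" between the arms, "with 90% power and a Bayesian posterior probability of 75% (of any reduction"). From this it concludes that "734 individuals (367 per group) will need to be diagnosed with GDM".

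Table 4 in section 7.2 is titled "Bayesian power to declare efficacy depending on level of evidence (probability threshold"). It lists the power for Prob(RR<1) to exceed each of six thresholds, from 70% to 95%. The highlighted row is the planned design: 0.25 versus 0.175, 367 per group.

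The analysis text of section 7.2 first plans a logistic model for the primary outcome: "We will report relative risks or group mean differences and 95% confidence intervals (CIs"). It then adds a Bayesian analysis with a neutral prior (RR 1.0, 95% credible interval 0.3 to 3.3), for which "we will report RR and 95% credible intervals and the probability of reduced adverse neonatal outcomes and costs". No posterior threshold is adopted there. The 75% appears only in the 7.1 sentence and as one of Table 4's six columns.

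**The concern.** The power in the sentence and the power in the table differ for the same rates, group size and threshold. A reader cannot tell whether the trial was sized for 75%, 90% or 95% posterior probability, or for 97%, 89% or 80% power.

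The second half follows from the first. Section 7.1 builds its case on a 75% posterior probability and Table 4 speaks of declaring efficacy, but the analysis plan does not say what result would count as success or which of its two analyses governs. If that is settled after the data are seen, the same result could be called positive or not. It also affects the interim look at 50% enrollment, where section 7.2 foresees a decision on adjusting the sample size: that decision needs one stated power and evidence level to aim at.

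**Working it through.** **Inputs.** Control rate 0.25, relative reduction 30% (treatment rate 0.25 × 0.70 = 0.175) and 367 per group come from section 7.1. The prior comes from section 7.2. I assume it is normal on log RR, so its SD is (ln 3.3 − ln 0.3)/(2 × 1.96) = 0.612. Success in Table 4 means Prob(RR<1) above the threshold. The row is read with power falling from the 70% to the 95% column, the only possible order, since a stricter threshold is harder to cross.

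**Reproducing Table 4.** With a flat prior, crossing threshold t is close to a one-sided test at level 1 − t:

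z = 0.075/√((0.25×0.75 + 0.175×0.825)/367) = 0.075/√((0.1875 + 0.1444)/367) = 2.494

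- 75%: Φ(2.494 − 0.674) = 0.966
- 90%: Φ(2.494 − 1.282) = 0.887
- 95%: Φ(2.494 − 1.645) = 0.802

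Exact binomial enumeration with a normal likelihood for log RR gives:

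| Threshold | Table 4 | Stated prior | Flat prior | Section 7.1 |
|---|---|---|---|---|
| 75% | 0.97 | 0.965 | 0.965 | 0.90 |
| 90% | 0.89 | 0.880 | 0.886 | – |
| 95% | 0.80 | 0.786 | 0.800 | – |

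The table reproduces to within 2 percentage points. The sentence misses by about 6.5 points (0.965 − 0.90).

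**Group size for the pair stated in 7.1.** n = (z_t + z_power)² × 0.3319/0.075² = 59.0 × (z_t + z_power)².

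- 90% power at 75%: 59.0 × (0.674 + 1.282)² = 226 per group; 237 by exact enumeration with the stated prior; 253 by the pooled formula with a continuity correction. All are well below 367.
- 90% power at 90%: 59.0 × (1.282 + 1.282)² = 388; 400 by exact enumeration with the stated prior. So 367 falls slightly short of this target.
- 80% power at 95%: the pooled-variance formula gives 366.8, which rounds up to 367.

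The last match suggests where 367 came from, and the 236, 294, 367 and 484 rows all show 0.80 at 95%. It is not proof. The same formula gives 484 for 0.20 versus 0.14, as tabulated, but 234 and 289 where the table has 236 and 294.

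**What each threshold would mean as a success rule.** With 25% in both arms and 367 per group, the chance of crossing the threshold is:

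| Threshold | Stated prior | Flat prior |
|---|---|---|
| 75% | 0.242 | 0.253 |
| 90% | 0.094 | 0.100 |
| 95% | 0.046 | 0.050 |

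A result just reaching 75% is 84 versus 92 events: RR = 84/92 = 0.913. The SE of log RR is √(1/84 + 1/92 − 2/367) = 0.132, so the 95% CI is 0.705 to 1.182. The posterior probability under the stated prior is 0.750.

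**If the two-sided 95% CI governs.** Power is Φ(2.494 − 1.960) = 0.703 (0.698 by exact enumeration), a figure the plan does not give.

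**The case against.** The strongest reply is that the slip is editorial and conservative. If 90% is read as a floor, 0.97 satisfies it, the sample size does not change, and the 95% CI analysis is untouched. There is also an innocent possible origin: section 7.1 says the sample size is being adjusted from an earlier 40% outcome rate, and the Table 4 rows for 60 and 120 per group at that rate both show 0.89 at 75%. The wording may have been carried over. On the success rule, reporting a posterior probability without a cut-off is a legitimate plan, and the logistic model is listed first. The 24-25% false-positive rate applies only if 75% is used as a decision rule, which section 7.2 does not do.

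Much of this stands, and it limits the weight of the point. But the sentence does not say at least 90%, and it presents 367 per group as the number needed for a pair that needs about 130 to 140 fewer (367 − 237 = 130; 367 − 226 = 141). A carried-over phrase would explain the error without correcting it. A purely descriptive posterior is acceptable, but the plan should say so, because 7.1 names a threshold and the Table 4 title refers to declaring efficacy.

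**Conclusion.** The concern holds. The power stated in section 7.1 is wrong for the threshold it names: 0.90 in the text against 0.97 in Table 4 and 0.965 on recomputation. Section 7.2 leaves open whether any posterior threshold defines success. The numerical contradiction is certain and does not depend on the choice of prior. The false-positive rates are conditional on the threshold being used as a rule, and they assume a 25% event rate and a normal prior on log RR.

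This discrepancy does not make the trial underpowered at 75% and does not by itself call for a different sample size. All figures take 367 analysed per group as given. Whether the 734 are people diagnosed with GDM or people screened is a separate question.

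**What to change.** In section 7.1, replace the power statement with the Table 4 pair that actually sized the trial: 97% at 75%, 89% at 90%, or 80% at 95%. Only the study team can confirm which. The 367 per group can stay; if 90% at a 90% threshold was intended, state the power as 89%.

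In section 7.2, say whether that threshold is the success rule or only descriptive, and how it relates to the logistic-model 95% CI. If it is the success rule, give its false-positive rate. All of this should be in place before the interim decision on sample size.

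The cost is one sentence in 7.1 and one or two in 7.2. The downside is presentational: the stated power may drop to 89% or 80%, or a false-positive rate of about 24-25% has to be shown beside the 75% threshold.

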1. BACKGROUND

Gestational diabetes (GDM) is a condition in which carbohydrate intolerance develops during pregnancy. It remains one of pregnancy's most common medical complications, afflicting approximately 10% of all pregnancies in the United States (1). GDM is associated with maternal and fetal complications such as hypertensive disorders of pregnancy, birth injury, fetal macrosomia, cesarean section, neonatal complications, and increased risk of developing diabetes later in life (2). In addition, the Hyperglycemia and Adverse Pregnancy Outcomes (HAPO) study found that maternal hyperglycemia is associated with adverse perinatal outcomes of increased birth weight and neonatal hyperinsulinemia (3, 4). Timely diagnosis and treatment of GDM improves both maternal and fetal outcomes (5, 6).

To avert the multitude of the complications associated with GDM, universal screening is recommended at 24-28 weeks gestation (5, 7). Currently, screening and diagnosis of GDM can be made through various glucose challenge tests (8). Table 1 lists the current recommendations by various policy for GDM screening (7, 9, 10).

Table 1: GDM Screening Recommendations

Organization (Year)	Test	Criteria for GDM
		diagnosis
American Diabetes	Universal screening	FPG ≥ 92 mg/dL
Association (2020)	One Step	1h PG≥ 180 mg/dL
	2h PG (75 g OGTT)	2h PG ≥ 153 mg/dL
	Or	Or
	Two Step	1h ≥ 135 or 140mg/dL
	1h GCT (50g OGCT)/3h	Fasting ≥ 95 or 105 mg/dL
	OGTT (100g)	1hr ≥ 180 or 190 mg/dL
		2hr ≥ 155 or 165 mg/dL
		3hr ≥ 140 or 145 mg/dL

American College of Obstetrics & Gynecology (2018)	Universal screening Two-Step 1h PG (50 g OGCT) 3hr (100g OGTT)	
National Institute for Health & Care Excellence (2015)	Targeted high-risk screening One step 2h PG (75 g OGTT)	FPG ≥ 100mg/dL 2hr PG ≥ 140 mg/dL
WHO & FIGO (2013)	Universal screening One step 2h PG (75g OGTT)	FPG ≥126 mg/dL 2 h PG≥200 mg/dL
International Association of the Diabetes and Pregnancy Study Group (2010	Universal screening One step 2h PG (75g OGTT)	FPG ≥ 92 mg/dL 1h PG≥ 180 mg/dL 2h PG ≥ 153 mg/dL

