Most institutions follow the American College of Obstetrics & Gynecology (ACOG) recommendations of a two-step assessment during 24 to 28 weeks gestation (2). However, there are at least four limitations of the 50g oral glucose tolerance test (GCT) diagnostic values. First, the one-hour GCT was validated to determine the risk of developing Type II diabetes later in life; the diagnostic cutoff, however, is not centered on preventing adverse maternal or fetal outcomes. Second, a positive one-hour GCT result requires pregnant people to return to the clinic while fasting to complete a three-hour glucose challenge test (GCT). Third, the predictive value changes in different ethnicities due to the varying prevalence of GDM (11). Fourth, there is no available screening test for people who present late to care or those who cannot tolerate the GCT (such as people after bariatric surgery or with significant nausea and vomiting). For those patients the most common management would be to panel their blood sugars for at least 1 week.

Other traditional diagnostic laboratory values, such as hemoglobin A1c and fasting blood glucose, used in non-pregnant states, have not been reliable or validated during pregnancy. HemoglobinA1c has poor sensitivity and specificity in the diagnosis of GDM, allowing for a high false-negative rate (12). Fasting blood glucose (FBG) was widely studied to decrease the burden associated with GTT, as it is associated with less cost and causes minor discomfort. However, no standardized criteria have been shown to provide reproducible GDM diagnosis (11).

Despite the high prevalence of GDM and complications, very few randomized trials studying the optimal screening test have been conducted (13). A recent randomized trial comparing the single step to the two-step diagnosis showed no difference in perinatal outcomes (14). A Cochrane review in 2015 cited that six small randomized control trials have been completed that have assessed optimal GDM screening. Of the six, only two studies compared the differences between recommended diagnostic tests (7). The findings are listed below.

Table 2: Randomized trials on screening for GDM

Title	RCT	N	Findings
Hillier et	RCT: 75g GTT v.	23,792	No difference in the primary outcome of a diagnosis of
al/2020 (14)	50g GCT/ 100g		GDM, LGA, CD, HDP, or perinatal composite
	GTT		
Olarinoye et	RCT: 75g GTT v.	248	Higher prevalence of GDM in 75g GTT group, No
al./2004 (12)	100g GTT		difference in macrosomia or FBG

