Shirazian et	WHO 75g GTT v.	670	No difference in diagnosis of GDM, CD, macrosomia,
al/2008 (15)	ADA 75g GTT		instrumental birth

In the U.S., trends of obesity, sedentary lifestyle, cardiovascular disease, and many other risk factors that place patients at high risk of developing GDM are continuing to soar (16). However, with the adverse outcomes associated with GDM for both mother and infant, there is an urgent need to develop a comprehensive and standardized form of screening and diagnosis.

Continuous Glucose Monitoring in pregnancy

Continuous glucose monitoring systems putatively measure interstitial glucose values throughout the day, providing measurements every five minutes wirelessly. Providers are given many glucose values, including the mean, fasting, and range of glucose levels. Unlike a point of care value such as FBG or GTT result, CGM allows for much greater surveillance and detection of hyperglycemic episodes (9). Target values can be programmed into the receiver or mobile app, allowing for calculating time in range.

Prospective studies evaluating the accuracy of CGM during GTT assessed the efficacy of CGM to detect hyperglycemic excursions (17). In addition, CGM has been studied in high-risk patient groups to identify hyperglycemic episodes. CGM has detected abnormal glucose profiles and provided caregivers specific glycemic trends in multiple populations at risk for abnormal glycemic trends, such as morbid obesity, critically ill, polycystic ovarian syndrome (9).

Current two-step testing has many limitations, such as requiring a second diagnostic test that requires specific timing and prolonged laboratory stay (4 hours) with further delaying treatment and diagnosis. Unfortunately, no current

#UTHealtl

IRB NUMBER: HSC-MS-22-0153 IRB APPROVAL DATE: 07/05/2023 data uses CGM as a screening tool for GDM. CGM is a promising, minimally invasive modality that will provide a more comprehensive evaluation of the glycemic profile of people. Thus, allowing a prompt diagnosis and treatment tailored to each person's glycemic discrepancies recorded by the CGM.

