2. RATIONALE FOR A CLINICAL TRIAL

There are multiple reasons for a clinical trial comparing the traditional method of screening for GDM versus

[figure not shown]
- Need for a diagnostic test that is based on maternal and neonatal outcomes.
- No current consensus on the best screening test for GDM during pregnancy.
- Non-pregnant diagnostic laboratory values, such as Hemoglobin A1c and fasting plasma glucose, do not have reliable diagnostic cut-offs during mid-pregnancy.
- Need for a test that can efficiently diagnose GDM, which does not require additional, lengthy clinic visits.
- The use of CGM permits for a complete glycemic profile as compared to the point of care glucose challenge test, thus allowing for a more specified and thorough treatment of GDM
- Readily available CGM results allow for prompt, individualized treatment.
- There are no current large, ongoing trials studying CGM as a screening tool for GDM.

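### Section 7.1 counts its 734 as people diagnosed with GDM, although the trial randomises and analyses everyone screened, and its 90% power at a 75% posterior probability disagrees with Table 4

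*Combined protocol and SAP*

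**What the plan says.** Section 7.1 assumes a 25% rate of the composite neonatal outcome and a 30% reduction. It plans the trial "with 90% power and a Bayesian posterior probability of 75% (of any reduction"), and concludes that "734 individuals (367 per group) will need to be diagnosed with GDM. With a 10% loss to follow up, 816 people in total" must be enrolled. It then divides 816 by an 80% enrolment rate to reach 1020 approached.

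Other sections describe a different population from the diagnosed one named there:

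- Sections 3.3 and 4.2 define participants as pregnant people undergoing GDM screening.
- Section 5.4 randomises them after consent to the glucose challenge or to CGM, so diagnosis comes after randomisation and by different criteria in each arm.
- Section 7.2 specifies intention to treat.
- Section 7.4 plans to recruit 816 people.

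Section 7.1 itself ties the 25% rate to the people to be enrolled: "In this trial we would include a more diverse population with a lower rate of factors associated with GDM".

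Table 4 gives Bayesian power by threshold for the posterior probability that RR is below 1. Its row for 25% versus 17.5% with 367 per group, the highlighted row, reads 0.98, 0.97, 0.95, 0.93, 0.89 and 0.80 at thresholds of 70, 75, 80, 85, 90 and 95%. Section 7.2 sets the prior: RR centred at 1.0 with a 95% credible interval of 0.3 to 3.3.

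**The concern.** The sample size sentence names a population that the design does not enrol. Read literally, the enrolment target cannot deliver the required number. It could also be taken to call for a comparison of diagnosed participants only. Because diagnosis follows randomisation and uses different criteria in each arm, that comparison would lose the protection of randomisation, and it is not the analysis in 7.2.

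The power statement is a separate error. A reader of 7.1 would believe that 367 per group was chosen to give 90% power at the 75% threshold. Table 4 does not show that, so the strength of evidence for which the trial was sized is unclear. The planned look at 50% enrolment, which may adjust the sample size, needs a definite population and a definite power target to work from.

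**Working it through.** **Inputs.** From 7.1: 734 total, 367 per group, 10% loss, 80% enrolment, 25% control rate, 30% reduction (25% × 0.70 = 17.5%). From 7.2: the prior and Table 4. From section 1: GDM "afflicting approximately 10% of all pregnancies in the United States".

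**1. Which population fits 816?**

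- 734 / 0.9 = 815.6, rounded up to 816. 816 / 0.8 = 1020. Both stated figures reproduce.
- 816 × 0.9 = 734.4 people followed up. For 734 of them to be diagnosed, 734 / 734.4 = 99.9% would need to have GDM.
- No step allows for the share of screened people who are diagnosed. The figures are coherent only if 734 is everyone randomised who has a known outcome.

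For scale on the literal reading: at the 10% national figure, 734 followed gives 734 × 0.10 = 73 cases, and 734 cases would need 734 / 0.10 / 0.9 = 8,156 enrolled. The trial's own diagnosis rate is not given. At an assumed 30% these become 734 × 0.30 = 220 and 734 / 0.30 / 0.9 = 2,719.

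**2. Does 367 per group give the stated power?**

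Prior SD of log RR = (ln 3.3 − ln 0.3) / (2 × 1.96) = 0.612, mean 0. For each possible pair of event counts x₁ (control) and x₂ (CGM), with n per group:

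- log RR estimate L = ln(x₂/x₁), variance v = 1/x₁ + 1/x₂ − 2/n
- posterior variance V = 1/(1/v + 1/0.612²), posterior mean m = V·L/v
- P(RR < 1) = Φ(−m/√V)

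Power is the total binomial probability of the pairs for which P(RR < 1) exceeds the threshold. The normal likelihood on log RR is an approximation, because 7.2 does not specify its binomial model in detail.

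| Threshold | Table 4, n = 367 | Recomputed, 25% vs 17.5% | Recomputed, no effect (25% vs 25%) |
|---|---|---|---|
| 70% | 0.98 | 0.975 | 0.290 |
| 75% | 0.97 | 0.965 | 0.242 |
| 80% | 0.95 | 0.949 | 0.192 |
| 85% | 0.93 | 0.924 | 0.144 |
| 90% | 0.89 | 0.880 | 0.094 |
| 95% | 0.80 | 0.786 | 0.046 |

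The table row reproduces within 2 percentage points, which also confirms which power belongs to which threshold. The 90% power at 75% in the text does not reproduce.

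**3. What would the stated pair need?**

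By the same method, the smallest n per group giving 0.90 power is 237 at the 75% threshold (0.9005) and 400 at the 90% threshold (0.9003).

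**4. What does 367 correspond to?**

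The usual two-proportion formula is n = [z₁₋α √(2p̄(1−p̄)) + z₁₋β √(p₁(1−p₁) + p₂(1−p₂))]² / (p₁ − p₂)². With one-sided α = 0.05, 80% power and p̄ = 0.2125:

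[1.645 × 0.5785 + 0.842 × 0.5761]² / 0.075² = 366.8, or 367.

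That is the 0.80 at 95% cell of Table 4. The 20% versus 14% row behaves the same way (483.6, printed 484). The formula gives 289.0 for the row printed as 294 and 233.3 for the row printed as 236, so this is a close coincidence and not proof of how the table was built.

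**The case against.** The strongest reply is that the documents already settle the population. The PICO statement, the enrolment arithmetic, the recruitment target and the intention-to-treat statement all point to everyone randomised, which makes the diagnosis clause a slip around a table that reproduces. That largely stands, and it is why no change to 816 is asked for. The clause is still wrong and sits in the sentence that states the sample size.

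It can also be said that the power pair errs on the safe side. That stands for the 75% threshold. A plausible origin is Table 4's row for 40% versus 28% with 120 per group, which prints 0.89 at 75%. The 40% is the earlier study's rate, and 7.1 says that the sample size is being adjusted. The pair may have been carried over, but the documents do not confirm it.

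Three stronger readings are tempting and are not supported:

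- *The trial is about tenfold too small (73 cases against 734).* This needs the diagnosed-only reading, which the plan's own arithmetic contradicts.
- *The power mismatch shows a shortfall.* It does not: Table 4 gives 0.97 at the threshold that 7.1 names.
- *The 30% reduction is refuted by the plan's own background.* The protocol does say that "A recent randomized trial comparing the single step to the two-step diagnosis showed no difference in perinatal outcomes", but none of the trials in its Table 2 tested CGM, so they neither support nor exclude 30%. Nor does the earlier observational study supply the figure: it reports an association of time above range with "higher rates of adverse neonatal outcomes of preterm birth, intravenous glucose therapy and longer hospitalization", not a treatment effect. The text presents 30% as a reduction to detect, which is a legitimate design target. Its missing rationale is missing detail, not an error.

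**Conclusion.** Two statements in 7.1 are wrong as written.

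The first is the population. 734 diagnosed participants cannot come from 816 people randomised before screening unless nearly all have GDM. The only reading consistent with 816, 1020, section 7.4 and intention to treat is 734 randomised participants with a known primary outcome. On that reading neither the enrolment target nor the analysis changes, and the 30% reduction applies on average to everyone randomised, including people without GDM by either method.

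The second is the power. The 90% at 75% pair conflicts with Table 4's 0.97 at 75%, 0.89 at 90% and 0.80 at 95%. It corresponds to about 237 per group, not 367. The size is not deficient at the 75% threshold. What is unclear is which threshold governs, and with no effect the chance of meeting it is about 24%, 9% or 5% at 75%, 90% or 95%. Section 7.2 undertakes to report the probability of benefit but names no threshold for declaring efficacy.

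The power figures rest on the stated rates and prior and on a normal approximation for log RR. The population conclusion needs no assumption about the diagnosis rate.

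**What to change.** In section 7.1:

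1. Replace the clause requiring the 734 to be diagnosed with wording such as: *will need to be randomised and have a known primary outcome, whatever their screening result*. State that the 25% rate and the 30% reduction refer to that intention-to-treat population. If the sponsor did mean diagnosed participants, state the expected diagnosis rate and reconcile both 816 and the intention-to-treat analysis with it.
2. Restate the power and threshold so that they agree with Table 4. Name which of 0.97 at 75%, 0.89 at 90% or 0.80 at 95% the trial was sized on, and say that this threshold will be used to declare efficacy.
3. Label the 30% as a design assumption across all randomised participants.

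The cost is wording in one section and possibly a less favourable stated power (0.89 or 0.80). If all randomised participants were meant, no patients or procedures are added.
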